### **11.1.2 Unexpected Adverse Event**

An expected AE is one for which the nature or severity is consistent with the known AE profile of the product. For a study drug, the known information is contained in the IB which includes the HP-5000 Developmental Core Safety Information.

An unexpected AE is one for which the specificity or severity is not consistent with the current IB and Developmental Core Safety Information.

Furthermore, reports that add significant information on specificity or severity of a known, already documented AE constitute unexpected events.

### **11.1.3 Serious Adverse Events**

A serious adverse event (SAE) is any untoward medical occurrence that at any dose:

- results in death

**NOTE:** Cause of death is required whenever known. If an autopsy was performed, an autopsy report should be provided. Death should usually be reported as the outcome of a specific SAE.

- is life-threatening.

**NOTE:** The term “life-threatening” in the definition of “serious” refers to an event in which the subject was at risk of death at the time of the event; it does not refer to an event which hypothetically might have caused death if it were more severe.

- Requires inpatient hospitalization or prolongation of existing hospitalization.

**NOTE:** An elective hospital admission to treat a condition present before exposure to the test drug, or a hospital admission for a diagnostic evaluation of an AE, does NOT qualify the condition or event as an SAE.

- Results in persistent or significant disability/incapacity.
- Results in a congenital anomaly in the offspring/fetus.

**NOTE:** A congenital anomaly in an infant born to a mother who was exposed to study drug during pregnancy is an SAE. However, a newly diagnosed pregnancy in a subject that has received a study drug is NOT considered an SAE but an AE.

- Is an important medical event.

**NOTE:** *Medical and scientific judgment should be exercised in deciding whether it is appropriate to consider other situations serious, such as important medical events that may not be immediately life-threatening or result in death or require hospitalization but may jeopardize the subject or may require intervention to prevent one of the other outcomes listed in the definition above. Examples of such events are: intensive treatment in an emergency room or at home for allergic bronchospasm, blood dyscrasias, or convulsions that do not result in hospitalization, development of drug dependency or drug abuse.*

## 11.2. Management of Adverse Events

Adverse events will be collected from the time of first dose administration through the Follow-up Visit or Early Termination Visit, whichever occurs first.

Subjects who complete the Double-blind Treatment Phase or terminate early will continue to be monitored for AEs for 30 days from last day for study treatment, unless resolution, they withdraw consent or are lost to follow-up.

### 11.2.1 Collection

The investigator is responsible for the detection and documentation of events meeting the criteria and definition of an AE or SAE described previously. At each visit, the subject will be allowed time to spontaneously report any issues since the last visit or evaluation. The investigator will then monitor and/or ask about or evaluate AEs using non-leading questions, such as:

- “How are you feeling?”
- “Have you experienced any issues since your last visit?”
- “Have you taken any new medications since your last visit?”

Any clinically relevant observations made during the visit will also be considered AEs.

### 11.2.2 Evaluation

#### 11.2.2.1 Severity of Adverse Events

The clinical severity of an AE will be classified as

Mild	Usually transient and may require only minimal treatment or therapeutic intervention. The event does not generally interfere with usual activities of daily living.
Moderate	Usually alleviated with additional specific therapeutic intervention. The event interferes with usual activities of daily living, causing discomfort but poses no significant or permanent risk of harm to the subject.
Severe	Interrupts usual activities of daily living, or significantly affects clinical status, or may require intensive therapeutic intervention.

It is important to distinguish between severe AEs and SAEs. Severity is a classification of intensity whereas an SAE is an AE that meets serious criteria, as described in [Section 11.1.3](#).

#### 11.2.2.2 Seriousness

The investigator is to evaluate whether the AE meets serious criteria, as described in [Section 11.1.3](#).

#### 11.2.2.3 Action Taken

Action taken may consist of:

Drug withdrawn	An indication that a medication schedule was modified through termination of a prescribed regimen of medication.
Dose interrupted	Patch temporarily removed
Dose not changed	No action taken with study drug
Not applicable	Determination of a value is not relevant in the current context.
Unknown	Not known, not observed, not recorded, or refused.

#### 11.2.2.4 Outcome at the Time of Last Observation

The outcome at the time of last observation will be classified as follows:

- Recovered/resolved
- Recovered/resolved with sequelae
- Recovering/resolving
- Not recovered/not resolved

- Fatal\*
- Unknown

**\*NOTE:** Only select fatal as an outcome when the AE results in death. If more than 1 AE is possibly related to the subject's death, the outcome of death should be indicated for each such AE. Although "fatal" is usually an event outcome, events such as sudden death or unexplained death should be reported as SAEs.

#### 11.2.2.5 Adverse Event Relationship to Investigational Product

The investigator must make an assessment of each AE's relationship to study drug. The categories for classifying the investigator's opinion of the relationship are listed below.

Not related	An AE with sufficient evidence to accept that there is no causal relationship to study drug administration (e.g., no temporal relationship to drug administration, because the drug was administered after onset of event; investigation shows that the drug was not administered; another cause was proven).
Unlikely related	An AE, including laboratory test abnormality, with a temporal relationship to study drug administration that makes a causal relationship improbable, and in which other drugs, events or underlying disease provide plausible explanations.
Possibly related	An AE with a reasonable time sequence to administration of the study drug, but which could also be explained by concurrent disease or other drugs or events. Information on drug withdrawal may be lacking or unclear.
Definitely Related	An AE occurring in a plausible time relationship to study drug administration, and which cannot be explained by a concurrent disease or other drugs or events. The response to withdrawal of the drug (dechallenge) is clinically reasonable.

Note: AEs at patch application site will be collected and marked with the flag in the eCRF to be able review and analyze them separately.

### **11.2.3 Documentation**

All AEs occurring within the period of observation for the study must be documented in the eCRF with the following information; where appropriate (The period of observation for the study is described in **Section 11.2**):

- AE name or term
- When the AE first occurred (start date and time)
- When the AE stopped (stop date and time or an indication of “ongoing”)
- Severity of the AE
- Seriousness (hospitalization, death, etc.)
- Actions taken
- Outcome
- Investigator opinion regarding the AE relationship to study drug

### **11.2.4 Treatment of Adverse Events**

Adverse events that occur during the study will be treated, as necessary, by established standards of care. If such treatment constitutes a deviation from the protocol, the subject should be withdrawn from the study and the reason and date of withdrawal must be documented in the eCRF. The decision about whether the subject may continue in the study will be made by the sponsor after consultation with the investigator and/or Medical Monitor.

If a subject experiences an intolerable AE , the investigator must decide whether to withdraw the subject from the study and/or treat the subject. Special procedures may be recommended for the specific study drug, such as the collection of a serum sample for determining blood concentrations of study drug, or treatment regimens, as appropriate.

It is **NOT** necessary to unblind a subject’s treatment assignment in most circumstances, even if an SAE has occurred. If unblinding is necessary, see **Section 9.5** for a description of the unblinding procedures.

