### **8.2.3 Premature Subject Withdrawal**

All subjects are free to withdraw from participation in the study at any time, for any reason, specified or unspecified, and without prejudice to further treatment. The criteria for enrollment are to be followed explicitly and if a subject who does not meet enrollment criteria is inadvertently enrolled, that subject should be withdrawn from the study and the Sponsor or CRO must be notified.

Subjects should not be asked to withdraw from the study because of experiencing AE, lack of efficacy, pregnancy, or lack of compliance to the clinical study protocol, etc. Those patients can stop their study treatments (for subjects who do not comply the protocol specified instructions and procedures, every effort will be made to keep them in the study after stopping treatment unless there is an adverse impact on subject safety). Discontinuation from study treatment does not automatically lead to a complete withdrawal from the study. Subjects discontinuing from study treatment are strongly encouraged to continue in the study up to the study completion (Follow-up Phone Visit, Week 13).

Subjects who decide they do not wish to remain in the study should NOT be considered withdrawn from the study UNLESS they withdraw their consent. Subjects are encouraged to return to all scheduled site and telephone visits, perform all procedures (including eDiary completion and blood draws) and follow the all requirements of the protocol (including the prohibited therapies), but without study treatment administration, until the end of the study (Follow-up Phone Visit, Week 13).

The reason for study treatment discontinuation and withdrawal from the study will be separately recorded. When the subject discontinues study treatment and/or withdraw from the study, the reason will be recorded in the medical records and eCRF using the below categories for discontinuation of study treatment and withdrawal from the study respectively.

The reasons will be grouped into three main categories: “study treatment related”, “not study treatment related”, and “uncertain” and more specific sub-categories will be described under each of the three main categories.

- Study treatment related
  - Lack of efficacy
  - Adverse events
  - Deviation from protocol (Please specify the deviation)
  - Other
- Not study treatment related
  - Adverse events
  - Prohibited Medication Use
  - Pregnancy
  - Deviation from protocol (Please specify the deviation)
  - COVID-19

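### Protocol 11.2.4 still makes study withdrawal the default when adverse-event treatment is a deviation, which contradicts the retention rule in 8.2.3 and creates avoidable missing WOMAC data

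*Protocol*

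**What the plan says.** Protocol 11.2.4 (Treatment of Adverse Events) allows adverse events to be treated by usual standards of care and then states: "If such treatment constitutes a deviation from the protocol, the subject should be withdrawn from the study". It adds: "The decision about whether the subject may continue in the study will be made by the sponsor", after consulting the investigator and/or Medical Monitor. For an intolerable event, "the investigator must decide whether to withdraw the subject from the study and/or treat the subject".

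The amended Protocol 8.2.3 (Premature Subject Withdrawal) takes the opposite line: "Subjects should not be asked to withdraw from the study because of experiencing AE, lack of efficacy, pregnancy, or lack of compliance". It separates the two decisions: "Discontinuation from study treatment does not automatically lead to a complete withdrawal from the study". For subjects who do not follow protocol instructions, "every effort will be made to keep them in the study after stopping treatment unless there is an adverse impact on subject safety". Subjects who stop treatment are encouraged to keep all visits through the Week 13 call.

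Two other places follow 8.2.3. Section 11.2.7 has a pregnant subject stop the patch but continue visits. Section 11.2.2.3 recognises an interrupted dose ("Patch temporarily removed") as an action short of stopping the drug.

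**The concern.** A site managing an adverse event will read 11.2.4, and there it finds study withdrawal as the default whenever the treatment deviates from the protocol. For an intolerable event, the option of stopping or interrupting the patch while staying in the study is not mentioned. A site that follows this section gives up WOMAC assessments that 8.2.3 was rewritten to keep. At stake are Week 12 scores in the primary and key secondary analyses, and post-event scores in the supplementary and most other secondary analyses.

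**Working it through.** The plan's only figure near this point is 80% power at two-sided 0.05 (Protocol 13.2, SAP 3.1). Effect size and sample size are redacted, so it cannot be reproduced, and the point does not depend on it. The check is mainly one of text.

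1. **Is the conflict current?** The protocol file holds a pre-amendment and an amended text. Section 11.2.4 is the same in both. Before the amendment, 8.2.3 allowed withdrawal for adverse events, need for a prohibited medication and non-compliance, so the sections agreed. The amendment rewrote 8.2.3, removed from 9.9 the discussion of a non-compliant subject's eligibility to continue, and changed 11.2.7 from study withdrawal to stopping treatment. Section 11.2.4 was not changed, so the conflict lies within the amended text.

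2. **Can the rule be triggered?** Reported skin irritation is an adverse event (10.3.2.4.2). Table 2 bars topical corticosteroids on the knee and sedating antihistamines, so treating a patch-site reaction with either is a deviation. Table 2 also bars opioids, NSAIDs and oral or intramuscular corticosteroids, so treatment of other events can trigger it. No frequency is given.

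3. **Does the analysis need these subjects withdrawn?** No. The ITT set uses all available data regardless of deviations (SAP 5.1), and prohibited medication is not one of the three intercurrent events (SAP 2.4). The SAP is silent on how to handle a score taken under such a drug.

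4. **What is lost at Week 12 in the primary analysis?**
 - *Would have stayed on the patch, or interrupted and resumed it in time:* if retained, an observed score enters the MMRM, provided no intercurrent event applies. If withdrawn, the score is missing at random (SAP 16.1.2), or falls under the zero-benefit rule (SAP 16.1.4) if the reason is coded study treatment related.
 - *Stops the patch, reason not coded as related:* a retained score is excluded because the patch has been off for more than 24 hours; after withdrawal it is missing. No change.
 - *Stops the patch, reason coded as related:* no change if zero benefit is assigned without a score, or if the patch-off exclusion prevails. If zero benefit needs an obtained score and prevails over that exclusion, withdrawal changes the value from zero benefit to missing at random. SAP 16.1.4 refers to the obtained score, and SAP 16.1.5 treats adverse-event and lack-of-efficacy dropouts as missing data. Both fit the second reading, but the plan does not settle it.

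5. **Other analyses.** The key secondary endpoints follow the primary rules (SAP 16.2.2). The supplementary analysis (SAP 16.1.6) and most of SAP 16.3 make no intercurrent-event adjustment, so they lose post-event scores whether or not the patch is on. The responder analysis in SAP 16.3.16 counts missing as non-response, so it changes only for subjects who would have responded.

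6. **Does the Early Termination WOMAC fill the gap?** It is collected (Protocol 10.1.5) and mapped to a visit by SAP Table A. The Week 8 window ends at Day 73 and Week 12 opens at Day 74. 74/84 = 0.881, or 73/84 = 0.869 with the +1 day convention of SAP 6.1. So for a withdrawal in about the first 87 to 88% of the treatment phase, that score informs an earlier visit and not Week 12.

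7. **Direction of bias, illustration only.** Take the reading in step 4 under which treatment-related discontinuers are affected, with zero benefit meaning zero change. Assume mean changes of −6 (active) and −5 (placebo), and shares qA and qP who stop for related reasons and are then withdrawn. Missing at random gives −6 − (−5) = −1. Zero benefit gives (1 − qA)(−6) − (1 − qP)(−5):
 - qA = 5%, qP = 2%: −5.70 + 4.90 = −0.80
 - qA = 5%, qP = 5%: −5.70 + 4.75 = −0.95
 - qA = 2%, qP = 5%: −5.88 + 4.75 = −1.13

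 Withdrawal moves the difference to −1. That enlarges the apparent effect in the first two cases and shrinks it in the third. The sign depends on arm-specific rates that the documents do not give.

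**The case against.** The strongest reply is that 11.2.4 does not force withdrawal. The sponsor decides on continuation, and the intolerable-event sentence leaves the choice to the investigator. That is true, and it softens the rule. But withdrawal remains the starting point, no criterion for continuing is given, and the direction is still opposite to 8.2.3.

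Several mitigations stand. The Early Termination visit collects WOMAC, laboratory tests and ECG. A follow-up call comes about 7 days later (10.1.4), and adverse-event monitoring runs for 30 days after the last treatment (11.2). A reader might infer that withdrawn subjects drop out of safety follow-up; the documents do not support that. What they lose is the later scheduled visits.

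A reader might also infer that sites will often code these withdrawals as study treatment related, which would bring in the zero-benefit rule. Adverse events and protocol deviations are listed under both the related and not-related headings in 8.2.3, and SAP 16.1.5 names deviation from protocol among related reasons, so the coding is possible. But 8.2.3 lists prohibited medication use only under the not-related heading, and that is the most specific code for the patch-site example.

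Finally, a score taken under an opioid, NSAID or systemic corticosteroid may be confounded. That stands. It calls for an analysis rule for such scores, not for removing the subject from the study.

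**Conclusion.** The inconsistency is real, current and worth correcting. Following 11.2.4 creates avoidable missing post-event WOMAC data, at least for subjects who would have stayed on or resumed the patch.

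Two stronger readings are not supported. One is that the primary-analysis cost falls solely on subjects who stay on the patch. That requires zero benefit to be assigned without an obtained score, or the patch-off exclusion to prevail, and the SAP states neither. The other is that the trial loses a known amount of power or is biased in a known direction. The number affected is not given, the sample-size inputs are redacted, and the sign depends on unknown rates by arm. No power gain is claimed for the fix. The case rests on contradictory site instructions and data lost for no analytic reason.

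**What to change.** Reword 11.2.4 so that adverse-event treatment that deviates from the protocol, or an intolerable event, leads to a decision on study treatment only: continue, interrupt or stop the patch. State that scheduled visits and WOMAC continue to Week 12, and follow-up to Week 13, unless consent is withdrawn or continued participation would harm the subject, in line with 8.2.3 and 11.2.7.

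Record the deviating medication with its dates; Protocol 9.10 and SAP 13 already provide for medication recording on the eCRF. Add one SAP sentence on how a WOMAC score taken under that medication is handled.

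The cost is one protocol paragraph, one SAP sentence and a site memo, with no new visits or assessments. The small downside is that some retained scores will be taken under prohibited medication, which the SAP sentence is there to address.

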### **11.2.5 Follow-up**

All ongoing SAEs at the time of discontinuation will be followed (up to a maximum of 30 days after the last dose of study drug) to a satisfactory resolution, or until it becomes stable, or until it can be explained by another known causes (i.e., concurrent condition or medication) and clinical judgment indicates that further evaluation is not warranted. All ongoing AEs at the time of discontinuation will be followed for up to 7 days. All findings relevant to the final outcome of an AE must be reported in the subject’s medical record and recorded on the eCRF page.

## 11.2.6 Reporting of Adverse Events

### 11.2.6.1 Serious Adverse Events

The investigator or designee must report all SAEs promptly to Noven Pharmacovigilance within 24 hours of first becoming aware of the event by completing, signing and dating the SAE Form (within the eCRF), verifying the accuracy of the information recorded in the form with the source documents.

**All SAEs, irrespective of relationship to study treatment, must be reported to Noven as soon as possible but no later than 24 hours using the appropriate SAE form within the eCRF.**

It is very important that the SAE form (within the eCRF) be filled out as completely as possible at the time of the initial report. This includes the investigator's assessment of causality. All SAEs must be followed to resolution, or if resolution is unlikely, to stabilization. Any follow-up information received on SAEs should be forwarded within 24 hours of its receipt. If the follow-up information changes the investigator's assessment of causality, this should also be noted on the follow-up SAE form (within the eCRF). If eCRF system is down or not accessible for the site, the "Noven Serious Adverse Event Reporting Form (Noven SAE form)" must be used for reporting to Noven Pharmacovigilance. The site should use the eCRF system as the primary means to notify of the SAE (initial or follow-up). The Noven SAE "paper" form should only be used as the back-up option for notification if the eCRF system is down.

If the situation where the Noven SAE "paper" form is to be used, **all SAEs, irrespective of relationship to study treatment, must be reported to Noven as soon as possible but no later than 24 hours to:**

Email: [REDACTED]

SAEs, regardless of causality assessment, must be collected through the Termination Visit and for 30 days following study drug discontinuation, whichever is longer.

Any SAE judged by the investigator to be related to the study treatment should be reported to the sponsor regardless of the length of time that has passed since study completion.

The written report should be submitted on the SAE form (within the eCRF) provided for this purpose. At the time of first notification, the investigator or designee should provide the following information, if available:

- Protocol number
- Reporter (study site and investigator)
- Subject's study number
- Subject's age
- Subject's gender
- Date of first dose of study drug
- Date of last dose of study drug, if applicable
- Adverse event term
- The seriousness criteria that were met
- Date of occurrence of the event
- A brief description of the event and outcome to date
- Any actions taken in response to the SAE
- Concomitant medication at onset of the event
- Relevant medical history information
- Relevant laboratory test findings
- Investigator's opinion of the relationship to study drug ("Is there a reasonable possibility that the study drug caused the SAE?")
- Whether and when the investigator was unblinded as to the subject's treatment assignment

Preliminary SAE reports and/or any missing or additional relevant information concerning the SAE should be provided to the recipients of the initial information as soon as possible on a follow-up SAE form (within the eCRF), together with the following information (AE, date of occurrence, subject number, study ID, study drug, and site number) including copies of hospital case reports, autopsy reports and other documents requested by the sponsor; this will allow the follow-up information to be linked to the initial SAE report.

The investigator is required to comply with applicable regulations (including local laws and guidance) regarding the notification of his/her health authorities, institutional review board (IRB), principal and coordinating investigators, study investigators, and institutions.

